CHG will be safe for use in a sample of infants 36 weeks PMA or older, and less than 2 months of age (48 weeks PMA) with a CVC as evidenced by an adverse event rate less than 10%.

Research Question 2:

Does twice weekly CHG baths lead to rising (cumulative) CHG blood levels, liver function tests (LFTs -AST/ALT) and Serum Creatinine over time in a sample of infants 36 weeks PMA or older, and less than 2 months of age (48 weeks PMA) with a CVC?

Hypothesis 2:

Twice weekly CHG baths do not lead to rising (cumulative) CHG blood levels, LFTs (AST/ALT)

and Serum Creatinine over time in a sample of infants 36 weeks PMA or older, and less than 2 months of age (48 weeks PMA) with a CVC.

Methods

Study Design: A pilot study using a single arm trial design.

Study Sample: Our convenience sample will include 50 infants. Infants admitted to the NICU or pediatric CICU will be eligible to participate.

Inclusion criteria.

- Greater than/equal to 36 weeks PMA (gestational age + chronological age)
- Less than/equal to 48 weeks PMA (gestational age + chronological age)
- Greater than/equal to 3 days of age
- Existing or soon to be placed, peripheral or surgical CVC
- Permission to participate in trial by attending physician
- Parent or legal guardian informed consent to participate in the trial

Exclusion criteria.

- Infant with a large open lesion or severe skin condition (i.e., Myelomeningocele, Gastroschisis, lymphatic malformation, open chest, ostomies and/or mucus fistulas or Icthyosis)
- Infants with active seizure disorders
- Infants with Hypoxic Ischemic Encephalopathy
- Infants with severe multi-system organ failure or Liver failure as defined by documentation of abnormal liver function tests: alanine aminotransferase (ALT) and aspartate aminotransferase (AST) Gamma-glutamyltransferase (GGT) and L-lactate dehydrogenase (LD).
- HCT \leq 28%: Respiratory support (mechanical ventilation, continuous positive airway pressure or high flow nasal cannula with FiO₂ > 25% Oxygen by nasal cannula > 1 liter/min) or HCT \leq 25%: No respiratory support.
- Infant with renal impairment as defined by: documented serum Creatinine greater than 0.7, renal disorders (renal agenesis, polycystic kidney disease, dysplastic kidneys, acute renal injury).
- Infants deemed clinically unstable by their physician such as patients that are extremely fragile and wouldn't tolerate the stimulation of the bathing process or those infants being considered for withdrawal of care.

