- Rub area to be cleansed with a back and forth motion
- Use 1 cloth for neck, arms, and legs (stopping at ankles to prevent wiping of feet/heels)
- Use second cloth for torso and back

CHG Bath Intervention. Subjects whose parents consent for this study will receive a CHG bath twice weekly. The CHG baths will be performed by 1 of 5 trained study nurses on each unit to ensure a standard bathing technique. Baths will be performed every Monday and Thursday during the day shift, for up to 12 weeks post enrollment or until the CVC is removed or the patient is discharged. Nurses will use pre-warmed 2% CHG impregnated non-sterile cloths from Sage Products Inc. CHG bath cloths will be pre-warmed to 100°F (37.8°C) in the warmers provided by Sage Products Inc. Baths will entail cleaning the infants with 2 CHG bathing cloths (1 package) beginning at the neck, working down the body toward the feet. Nurses will be instructed not to use the CHG cloths on the face, scalp, or over open body orifices or wounds, including the genitalia and anus (where bloodstream absorption is enhanced). The genital and anal areas will be protected by placing a clean diaper on the study subject prior to initiation of CHG bath. Cleansing of the feet/heels with CHG will be avoided due to the possibility of blood sample contamination as explained by Cowen et al (1979). Nurses will document completion of the CHG baths on the CHG Bath Data Collection Tool that will be kept at each participant's bedside. When a bath needs to be delayed for clinical reasons, it will be done as close to the scheduled time as possible.

Cleansing between CHG baths: Cleansing of infants between CHG baths may be required if they become soiled. These baths or partial baths will be done per NICU standard of care using (non-CHG) Comfort Cloths by Sage Products Inc. and documented on the CHG Exposure and Comfort Cloth Bath Log (Appendix C).

CHG Exposure: Infant participants have the potential for additional CHG exposures for central line insertions, dressing changes, and perioperative bathing. Additional CHG exposures will be recorded on the CHG Exposure and Comfort Cloth Bath Log.

Monitoring for Adverse Events

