Random observations of CHG baths will be performed throughout the entire study period by a designated clinician to ensure that all nurses are bathing the infants using the same technique. Each study team member actively bathing study subjects will be audited a minimum of once every two months. These observations will be documented on the CHG Bath Audit Tool (Appendix K) and scores of 15/15 points are acceptable. Any score lower than 15 will require retraining on the bathing technique. Also to facilitate reliable assessment of skin lesions, a CHG Erythema Assessment Tool (Appendix L) will be available for nurses to follow during their assessments (maintained at each study patients' bedside) (Figure 1.).

The sponsor-investigator will also engage the services of a qualified independent monitor to ensure the protection of the rights of human subjects, the safety of all subjects involved in the investigation and the quality and integrity of the data resulting from the trial. The independent monitor will conduct a pre-monitoring set-up visit and a monitoring visit after every fifth patient has been recruited and on the study for 1 week.

Data Analysis. With the support of a faculty statistician from the BCH Center for Patient Safety and Quality Research, we will use descriptive statistics including mean, median, range, and frequencies to describe the study sample and the findings (skin findings and adverse events). We will characterize the study sample on demographic and clinical characteristics. Our primary outcome measures will be proportion of subjects that experience any adverse event, and the rate of adverse events per 100 patient-days of follow-up. Our inferential statistics will calculate 95% confidence intervals around these estimates.

Research Question 1:

Are twice weekly CHG baths safe for use in a sample of infants 36 weeks PMA or older, and less than 2 months of age (48 weeks PMA) with a CVC?

Data Analysis 1:

Descriptive statistics including mean, median, range and frequencies will be used to describe adverse events (including skin reactions and other untoward events). We will characterize the demographic and clinical characteristics of subjects that experience adverse events, although we will not perform hypothesis tests of association. We will consider time-to-rash data using Kaplan-Meier estimators.

Research Question 2:

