Does twice weekly CHG baths lead to rising (cumulative) CHG blood levels, liver function tests (LFTs -AST/ALT) and Serum Creatinine over time in a sample of infants 36 weeks PMA or older, and less than 2 months of age (48 weeks PMA) with a CVC?

Data Analysis 2:

Descriptive statistics including mean, median, range and frequencies will be used to describe CHG, LFTs and serum Creatinine blood levels over time. We will examine scatterplots and other graphical analysis of blood level dispersion over time to look for relationships.

Sample Size Justification. The primary quantitative goal of this study is estimation of the adverse event rate per 100 patient days. The study sample size will impact the precision of this estimate, and we will establish an upper bound on the rate if zero adverse events occur. In this context, we designed the study sample to expand the existing knowledge base.

Based on recent safety data (Quach, et al 2014) on roughly 200 neonates which recorded no adverse events, we assume the rate of adverse events using CHG bath is lower than 5 events per 1000 days of post-exposure follow-up. We propose following N=50 subjects over 7 days of post-exposure follow-up, for a total of 350 observation days. Assuming rates of 3.5 events or 1.0 events per 1000 days of follow-up, the probability that at least one subject will experience an adverse event is roughly 83% or 40% respectively. Using Monte Carlo simulations, the mean upper bound for estimable rates is 5.5 events per 1000 days.

Auditing and Inspecting:

The sponsor-investigator will permit study-related monitoring, audits, and inspections by the Boston Children's Hospital IRB, the independent data monitor and government regulatory bodies, of all study related documents (e.g. source documents, regulatory documents, data collection instruments, study data etc.). The Investigator will ensure the capability for inspections of applicable study-related facilities.

Human Subjects:

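### The mean upper bound of 5.5 events per 1000 days cannot be reproduced as stated and is out of reach of exact Poisson 95% limits on the planned 350 observation days; the adjoining 83% and 40% do not fit 350 days either

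*Combined protocol and SAP*

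**What the plan says.** All the planning figures stand in the Sample Size Justification. The target is a rate: "The primary quantitative goal of this study is estimation of the adverse event rate per 100 patient days". The person-time is explicit: "We propose following N=50 subjects over 7 days of post-exposure follow-up, for a total of 350 observation days". The true rate is assumed to lie below 5 per 1000 days. For rates of 3.5 and 1.0 per 1000 days, the plan says that "the probability that at least one subject will experience an adverse event is roughly 83% or 40% respectively". For the case of no events it promises that "we will establish an upper bound on the rate if zero adverse events occur". The precision statement follows: "Using Monte Carlo simulations, the mean upper bound for estimable rates is 5.5 events per 1000 days".

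The confidence level appears only under Data Analysis: "Our inferential statistics will calculate 95% confidence intervals around these estimates". Neither section names an interval method, says whether the bound is one-sided or two-sided, gives the true rate or rates simulated, or defines an estimable rate. The rates 3.5 and 1.0 are attached to the probability statement, not to the simulation.

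**The concern.** The figure of 5.5 is the only precision statement for what the plan calls its primary quantitative goal. It is lower than the smallest value that an exact Poisson 95% upper limit can take on 350 days. It also sits just above the assumed ceiling of 5 per 1000 days. A reader could therefore conclude that 50 infants followed for a week come close to confirming that ceiling. With exact limits they do not, even if no infant has an event.

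The sentence just before it raises a second doubt. The two probabilities depend only on the rates and the person-time given beside them, and they do not agree with 350 days. If the paragraph mixes two person-time totals, the reader cannot tell which one lies behind 5.5.

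**Working it through.** **Inputs.** T = 350 days (50 × 7), rates 3.5 and 1.0 per 1000 days, stated probabilities 83% and 40%, and stated bound 5.5, all from the Sample Size Justification. The 95% level is from Data Analysis. The event count X is taken as Poisson with mean rate × T: 0.35 at rate 1.0 and 1.225 at rate 3.5. All limits below are per 1000 days.

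**1. Trying to reproduce 5.5 at 350 days.** No method is given, so several were tried. These come near:

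- Two-sided square-root-transformed limit, (√x + 0.98)²/T. For x = 0, 1, 2, 3 it is 2.74, 11.20, 16.38 and 21.02. Weighting by Poisson(0.35) probabilities 0.7047, 0.2466, 0.0432 and 0.0050, plus a small tail, gives 1.93 + 2.76 + 0.71 + 0.11 + 0.01 = 5.52. At rate 3.5 the same method averages 11.29.
- Wald limit, (x + z√x)/T, averaged over several rates: 5.12 one-sided or 5.66 two-sided over the rates 1.0 and 3.5; 5.59 or 6.19 over rates spread evenly from 0 to 5. At a single rate it gives 2.49/2.78 (rate 1.0) and 7.74/8.55 (rate 3.5).
- One-sided Jeffreys limit at exactly zero events: 5.49. This is not a simulated mean; its mean is 7.42 at rate 1.0 and 11.83 at rate 3.5.

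**2. Behaviour at zero events, where the plan promises a bound.** The Wald limit is 0. The square-root limit is 0.98²/350 = 2.74, and with a true rate just above 2.74, zero events occur with probability exp(−0.00274 × 350) = 38%. For any method that returns 5.5 after zero events in 350 days, a true rate just above 5.5 gives zero events with probability exp(−0.0055 × 350) = exp(−1.925) = 14.6%. So 5.5 is there about an 85% one-sided bound.

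**3. Exact Poisson limits.** Upper limit = χ²(1 − a; 2(x + 1)) / (2T), with a = 0.05 one-sided and 0.025 two-sided. At x = 0:

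- one-sided: 2.996/350 = 8.56
- two-sided: 3.689/350 = 10.54

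The limit rises with x, so these are the smallest values it can take, and no true rate can bring the mean down to 5.5. For the two-sided mean at rate 1.0, the limits at x = 0, 1, 2, 3 are 10.54, 15.92, 20.64 and 25.05. The weighted sum is 7.43 + 3.93 + 0.89 + 0.13 + 0.01, about 12.4. All results, one-sided/two-sided:

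| Days | Zero events | Mean, rate 1.0 | Mean, rate 3.5 |
|---|---|---|---|
| 350 | 8.56 / 10.54 | 10.28 / 12.38 | 14.33 / 16.72 |
| 500 | 5.99 / 7.38 | 7.69 / 9.21 | 11.65 / 13.43 |

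Simulation agrees with the summed means. An exact zero-event limit of 5.5 would need 2.996/0.0055 = 545 days one-sided or 3.689/0.0055 = 671 days two-sided.

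**4. The adjoining probabilities.** P(at least one event) = 1 − exp(−rate × T).

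- 350 days: 1 − exp(−1.225) = 70.6% and 1 − exp(−0.35) = 29.5%
- 500 days: 82.6% and 39.3%

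Solving for T from the stated values gives −ln(0.17)/0.0035 = 506 days and −ln(0.60)/0.001 = 511 days. The two stated probabilities agree with each other, but not with 350 days.

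**The case against.** The best defence is that 5.5 can be reached. The two-sided square-root limit gives 5.52 using only the plan's 350 days, its 95% level and a rate that it names, 1.0. The undefined term in the precision sentence could also mean an average over a range of rates, and Wald limits averaged over 0 to 5 come close. Besides, the 95% level is stated for the final analysis and not for the simulation. This stands. A reader might infer that 5.5 is an arithmetic error, or that it is too small by a factor of about two. The documents do not support that, because they do not show how it was obtained. What the defence does not do is make 5.5 a usable bound. The square-root and Wald limits fail at zero events, and several unrelated methods landing near the same value is itself a reason to name the one used.

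A second stronger reading is that the whole paragraph was computed at about 508 days. The probabilities fit that, but even at 500 days the exact limits stay above 5.5, so it is not established.

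It is also fair to say that little hangs on 5.5. Hypothesis 1 uses an adverse event rate below 10%. Baths continue "for up to 12 weeks post enrollment or until the CVC is removed or the patient is discharged", so the final interval may rest on more than 7 days per infant. Purely as an assumption, if time on study equalled the 12.7-day average NICU stay given under Setting, 50 × 12.7 = 635 days would give exact zero-event limits of 4.7/5.8, either side of 5.5. The mean limits would still be 6.4/7.6 at rate 1.0 and 10.3/11.8 at rate 3.5. This lowers the severity; it does not support the sentence, which is tied to 350 days. Finally, preferring exact limits is a choice, and another named method valid at zero events would serve.

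**Conclusion.** The point holds in a limited form. The bound of 5.5 cannot be reproduced from what the plan states, and exact Poisson 95% limits on 350 days cannot deliver it at any true rate. In the plan's own unit, 5.5 is 0.55 per 100 patient-days, while the exact two-sided limit after zero events is 1.05. The size of any error in 5.5 itself cannot be fixed, because its method is unknown. The 83% and 40% are firmer: with the plan's stated inputs they should be 70.6% and 29.5%.

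These results assume a Poisson count with a constant rate, a 95% level for the bound, and the 350 days stated. A reader might infer that the trial will reach a wrong safety conclusion. The documents do not support that: no decision rule uses 5.5, and the final interval will be computed from the follow-up actually observed. The harm is an overstated expected precision. It should be corrected, at low severity, and treated as one point with the mismatch in the probabilities.

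**What to change.** Make one edit to the Sample Size Justification and a matching one to Data Analysis.

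1. Reconcile the observation days with the probabilities. If 350 days is right, give 70.6% and 29.5%. If about 500 days was intended, say how it arises and give 82.6% and 39.3%.
2. Replace the 5.5 sentence with a bound from a named 95% method that is valid at zero events. Possible text for 350 days: *With exact Poisson two-sided 95% intervals, zero events in 350 days gives an upper limit of 10.5 per 1000 days (1.05 per 100 patient-days); the mean upper limit is 12.4 if the true rate is 1.0 and 16.7 if it is 3.5 per 1000 days.* For 500 days the figures are 7.4 (0.74 per 100 patient-days), 9.2 and 13.4. If another method valid at zero events was used, state its name, level, sidedness and simulated rate or rates, and recompute.
3. In Data Analysis, name the same interval for the primary rate.

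The cost is wording only, with no extra patients or visits. The downside is that the stated precision becomes less favourable.
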